10.4.4. Reporting of SAEs

SAE Reporting to Alexion via an Electronic Data Collection Tool

- All SAEs will be recorded and reported to Alexion immediately and within 24 hours of awareness.
- The primary mechanism for reporting an SAE to Alexion will be the EDC system.
- If the electronic system is unavailable or site staff is unable to process the SAE via the EDC system at the time that the Investigator or site becomes aware of an SAE, the site will use the paper Contingency Form for SAE Reporting via facsimile or email. Facsimile transmission or email may also be used in the event of electronic submission failure.
 - Email: [contact] or Fax: [name]
- The site will enter the SAE data into the EDC system as soon as it becomes available.
- When further information becomes available, the EDC should be updated immediately with the new information and an updated SAE report should be submitted to Alexion Global Patient Safety (GPS) within 24 hours of Investigator/site awareness.
- After the participant has completed the study, no new data or changes to existing data are expected to be entered in the EDC system.
 - o If a site receives a report of a new SAE from a study participant which the Investigator considers to be related to the study intervention, or the site receives updated data on a previously reported SAE after the EDC system has been taken offline, then the site can report this information on a paper Contingency Form for SAE Reporting via facsimile or email.

10.4.5. Unexpected Events

Apart from the reporting of SUSARs, there may be other events which are relevant in terms of benefit-risk balance and which should be reported in a timely manner according to regional and national requirements. It is important for participant safety that, in addition to SAEs and reactions, all unexpected events that might materially influence the benefit-risk assessment of the study intervention or that would lead to changes in the administration of the study intervention or in overall conduct of a clinical study should be reported. Examples of such unexpected events include an increase in the rate of occurrence of expected serious adverse reactions which may be clinically important, a significant hazard to the patient population, such as lack of efficacy of a medicinal product, or a major safety finding from a newly completed animal study (such as, carcinogenicity).

Under the EU CTR 536/2014 (49), where unexpected events require an urgent modification of a clinical study, Alexion and the Investigator may need to take urgent safety measures without awaiting prior authorization. If such measures constitute a temporary halt of the clinical study, Alexion will apply for a substantial modification before restarting the clinical study.

10.5. Medication Error, Drug Abuse, and Drug Misuse

Medication Error

For the purposes of this clinical study, a medication error is an unintended failure or mistake in the treatment process for study intervention that either causes harm to the participant or has the potential to cause harm to the participant.

Any events of medication error, with or without associated AEs, are to be captured and forwarded to Alexion Global Patient Safety via email or facsimile ([contact] or [name]) using the Alexion Clinical Study Medication Error Report Form.

A medication error is not lack of efficacy of the drug, but rather a human or process related failure while the drug is in control of the study site staff or participant.

Medication error includes situations where an error:

- Occurred
- Was identified and intercepted before the participant received the drug
- Did not occur, but circumstances were recognized that could have led to an error

Examples of events to be reported in clinical studies as medication errors:

- Drug name confusion
- Dispensing error, eg, medication prepared incorrectly, even if it was not actually given to the participant
- Drug not administered as indicated, eg, wrong route, wrong device, or wrong site of administration
- Drug not stored as instructed, eg, kept at room temperature when it should be stored in the refrigerator
- Wrong participant received the medication (excluding IRT errors)
- Wrong drug administered to participant (excluding IRT errors)

Examples of events that **do not** require reporting as medication errors in clinical studies:

- Errors related to or resulting from IRT including those which led to one of the above listed events that would otherwise have been a medication error
- Participant accidentally missed drug dose(s), eg, forgot to take medication
- Accidental overdose (will be captured as an overdose)
- Participant failed to return unused medication or empty packaging

Medication errors are not regarded as AEs but AEs may occur as a consequence of the medication error.

Drug Abuse

For the purpose of this clinical study, drug abuse is defined as the persistent or sporadic intentional, nontherapeutic excessive use of study intervention for a perceived reward or desired nontherapeutic effect.

Any events of drug abuse, with or without associated AEs, are to be captured and forwarded to Alexion Global Patient Safety via email or facsimile ([contact] or [name]) using the Alexion Clinical Study Drug Misuse or Drug Abuse Report Form. This form should be used both if the drug abuse happened in a study participant or if the drug abuse involves a person not enrolled in the study (such as a relative of the study participant).

Drug Misuse

Drug misuse is the intentional and inappropriate use (by a study participant) of study intervention for medicinal purposes outside of the authorized product information, or for unauthorized study intervention, outside the intended use as specified in the protocol, including deliberate administration of the product by the wrong route.

Events of drug misuse, with or without associated AEs, are to be captured and forwarded to Alexion Global Patient Safety via email or facsimile ([contact] or [name]) using the Alexion Clinical Study Drug Misuse or Drug Abuse Report Form. This form should be used both if the drug misuse happened in a study participant or if the drug misuse involves a person not enrolled in the study (such as a relative of the study participant).

Examples of drug misuse include but are not limited to:

- The drug is used with the intention to cause an effect in another person
- The drug is sold to other people for recreational purposes
- The drug is used to facilitate assault on another person
- The drug is deliberately administered by the wrong route
- Only half the dose is taken because the study participant feels that he/she is feeling better when not taking the whole dose
- Someone who is not enrolled in the study intentionally takes the drug

10.6. Contraceptive Guidance and Collection of Pregnancy Information

10.6.1. Definitions

Woman of Childbearing Potential (WOCBP)

A woman is considered fertile following menarche and until becoming postmenopausal unless permanently sterile (see below).

If fertility is unclear (eg, amenorrhea in adolescents or athletes) and a menstrual cycle cannot be confirmed before first dose of study intervention, additional evaluation should be considered.

Women in the Following Categories Are Not Considered WOCBP

- 1. Premenarchal
- 2. Premenopausal female with one of the following:
 - Documented hysterectomy
 - Documented bilateral tubal ligation or bilateral salpingectomy
 - Documented bilateral oophorectomy

For individuals with permanent infertility due to an alternate medical cause other than the above, (eg, Mullerian agenesis, androgen insensitivity), Investigator discretion should be applied to determining study entry.

Note: Documentation can come from the site personnel's review of the participant's medical records, medical examination, or medical history interview.

- 3. Postmenopausal female
 - A postmenopausal state is defined as no menses for 12 months without an alternative medical cause prior to the Day 1 Visit.
 - A high follicle-stimulating hormone (FSH) level in the postmenopausal range may be used to confirm a postmenopausal state in women not using hormonal contraception or hormone replacement therapy (HRT). However, in the absence of 12 months of amenorrhea, confirmation with more than 1 FSH measurement may be required. In the absence of 12 months of amenorrhea the reason for not obtaining FSH levels should be documented by the Investigator at the time of Screening.
 - Females on HRT and whose menopausal status is in doubt will be required to use one of the non-estrogen hormonal highly effective contraception methods if they wish to continue their HRT during the study. Otherwise, they must discontinue HRT to allow confirmation of postmenopausal status before study enrollment.
- 4. Permanent sterilization at least 6 weeks prior to the Day 1 Visit.

10.6.2. Contraception Guidance

Contraceptive use by male or female participants should be consistent with local regulations regarding the methods of contraception utilized for those participating in clinical studies. If

teratogenic effects are suspected to be transferred to a fetus/embryo from a female spouse/partner of a male participant, pregnancy follow-up information will be obtained for the partner who becomes pregnant (refer to Section 10.5.3.1). In these cases, follow-up will be conducted on the pregnant partner in the same manner as a female participant who becomes pregnant during the study.

10.6.2.1. Guidance for Female Participants

Female participants of childbearing potential must use a highly effective or acceptable method of contraception, including at least 1 of the following until at least 8 months after the final dose of study intervention.

- 1. Intrauterine device in place for at least 6 weeks prior to first dose of study intervention.
- 2. Progestogen-only hormonal contraception associated with inhibition of ovulation (either oral, injectable, or implantable) for at least 6 weeks prior to first dose of study intervention.
- 3. Intrauterine progestogen releasing system for at least 6 weeks prior to first dose of study intervention.
- 4. Bilateral tubal occlusion for at least 6 weeks prior to first dose of study intervention.
- 5. Combined (estrogen- and progestogen-containing) hormonal contraception (either oral, intravaginal, or transdermal) for at least 6 weeks prior to first dose of study intervention.
- 6. Surgical sterilization of the male partner (medical assessment of azoospermia is required if vasectomy was performed within 6 months prior to first dose of study intervention). Male partner is still required to use condom during sexual intercourse.
- 7. Sexual abstinence for female participants:
 - a. Sexual abstinence is considered a highly effective method only if defined as refraining from heterosexual intercourse. In this study, abstinence is only acceptable if consistent with the participant's preferred and usual lifestyle. Abstinent female participants must refrain from heterosexual intercourse for at least 8 months after the final dose of study intervention.

Other methods of contraception that are not considered as highly effective for female participants, but are acceptable birth control methods (that result in a failure rate of more than 1% per year) include:

- 8. Progestogen-only oral hormonal contraception, where inhibition of ovulation is not the primary mode of action;
- 9. Male or female condom with or without spermicide
- 10. Cap, diaphragm, or sponge with spermicide
- 11. A combination of male condom with cap, diaphragm, or sponge with spermicide (double-barrier methods)

Female participants must not donate ova from the Day 1 Visit at least until 8 months after their final dose of study intervention.

The following methods of contraception are considered unacceptable in this study:

- Periodic abstinence (calendar, symptothermal, or post-ovulation methods
- Withdrawal (coitus interruptus)
- Spermicides only
- Lactational amenorrhea method
- Female condom and male condom should not be used together

10.6.2.2. Guidance for Male Participants

Contraception is the responsibility of the heterosexually active male participants in the study, regardless of his female partner's method of contraception.

Male participants who have had a vasectomy > 6 months prior to the first dose of study intervention must use a condom during heterosexual intercourse. Male participants who have had a vasectomy < 6 months prior to the first dose study intervention and those who have not had a vasectomy must use a condom and spermicide during heterosexual intercourse for at least 8 months after their final dose of study intervention.

Participants with a spouse/partner of childbearing potential or a pregnant or breastfeeding spouse or partner must agree to use double barrier contraception (male condom plus appropriate barrier method for the female partner) while on treatment and for at least 8 months after the last dose of study intervention. Double barrier contraception is required even with documented medical assessment of surgical success of a vasectomy.

Male participants must not donate sperm from the Day 1 Visit until 8 months after their final dose of study intervention.

10.6.2.2.1. Sexual Abstinence for Male Participants

Sexual abstinence is considered a highly effective method only if defined as refraining from heterosexual intercourse. In this study, abstinence is only acceptable if consistent with the participant's preferred and usual lifestyle. Abstinent male participants who become heterosexually active must use a condom and spermicide during intercourse.

Periodic abstinence (eg, calendar, symptothermal, or post-ovulation methods for a female partner) is not considered a highly effective method of contraception for male participants.

10.6.3. Collection of Pregnancy Information

Pregnancy data will be collected during this study for all female participants and female spouses/partners of male participants from the first dose of study intervention until the EOS Visit.

Any female participant who becomes pregnant during the study should be discontinued from the study intervention.

Exposure during pregnancy (also referred to as exposure in utero) can be the result of either maternal exposure or transmission of study intervention via semen following paternal exposure. If a female participant or a male participant's female spouse/partner becomes pregnant during the

conduct of this study, the Investigator must submit the "Pregnancy/Breastfeeding Reporting and Outcome Form" to Alexion GPS via facsimile or email. When the outcome of the pregnancy becomes known, the form should be updated and submitted to Alexion GPS. If additional follow-up is required, the Investigator will be requested to provide the information.

Exposure of an infant to study intervention during breastfeeding must also be reported (via the "Pregnancy/Breastfeeding Reporting and Outcome Form") and any AEs experienced by the infant must be reported to Alexion GPS via email or facsimile.

Pregnancy is not regarded as an AE unless there is a suspicion that the study intervention may have interfered with the effectiveness of a contraceptive medication. However, complications of pregnancy and abnormal outcomes of pregnancy are AEs and may meet the criteria for an SAE (eg, ectopic pregnancy, spontaneous abortion, intrauterine fetal demise, neonatal death, or congenital anomaly). Elective abortions without complications should not be reported as AEs.

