Abbreviations: 30s CST = 30-second Chair Stand Test; ADA = antidrug antibody; AE = adverse event; CDA-IGA = Cutaneous Dermatomyositis Activity Physician's Global Assessment; CDASI = Cutaneous Dermatomyositis Disease Area and Severity Index; CSM = core set measures; D = day; DM-DSQ = Dermatomyositis Disease Symptoms Questionnaire; ECG = electrocardiogram; eCRF = electronic case report form; EOS = end of study; EQ-5D-5L = European Quality of Life Health 5-item questionnaire dimensions 5 level; ET = Early Termination; FACIT = Functional Assessment of Chronic Illness Therapy; HAQ = Health Assessment Questionnaire; IMACS-TIS = International Myositis Assessment and Clinical Studies-Total Improvement Score; MDAAT = Myositis Disease Activity Assessment Tool; MMT-8 = Manual Muscle Testing subset of 8 muscles; OLE = Open-Label Extension; PD = pharmacodynamic(s); PK = pharmacokinetic(s); PROMIS = Participant-reported Outcomes Measurement Information System; SF-36 = Short Form Health Survey (36 questions version; UV = Unscheduled Visit; W = week(s); WOCBP = women of childbearing potential

Table 4: Schedule of Activities: Open-Label Extension Period for Part A (Phase 2) – Week 108 – Week 156

| Period | | | Open-L | abel Exte | nsion Per | iod | | UV | Notes |
|--|-----------|--------|--------|-----------|-----------|-------|---------------|----|---|
| Visit | 17 | 18 | 19 | 20 | 21 | 22 | 23/ ET/EOS | | OLE Period begins at the start of dosing on Day 183 Participants who discontinue/withdraw from the study should complete the ET Visit 8 weeks after the participant's last dose of study |
| Days | D757 | D813 | D869 | D925 | D981 | D1037 | D1079 | | intervention. In addition, a follow-up phone call 21 weeks (± 1 week) |
| Weeks | W108 | W116 | W124 | W132 | W140 | W148 | W156 | | after the participant's last dose of study intervention will be performed to collect information on concomitant medications, non-pharmacologic |
| Window (day) | ± 3 | ± 3 | ± 7 | ± 7 | ± 7 | ± 7 | ± 7 | | therapies and procedures, and AEs (see Section 7.2 for more details). |
| Weight | X | X | X | X | X | X | X | | |
| Vital signs | X | X | X | X | X | X | X | X | On dosing days, vital signs will be taken before study intervention administration and after the participant has been resting for at least 5 minutes (see Section 8.2.4). |
| Physical Examination | | | | | | | | X | |

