| | Only 2 patients have been identified with treatment-emergent ADA across ravulizumab clinical studies in all indications tested to date. There was no association or impact of immunogenicity on PK, safety, or efficacy in either of these patients. | |
| Pregnancy exposure/lactation | No studies of ravulizumab have been conducted in pregnant or breastfeeding women. There are no data available on excretion of ravulizumab in breast milk. | Pregnant or nursing female participants will be excluded from this clinical study. Women and men enrolled in the study, and their spouses/partners, must use a highly effective or acceptable method of contraception during treatment and for a period of 8 months following the final dose of study intervention. Breastfeeding should be discontinued during treatment and up to 8 months after treatment with ravulizumab (Section 10.5). |

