4.1.1. Part A (Phase 2 Portion)

There will be 3 periods in Part A of this study: Screening Period, Randomized Controlled Period, and OLE Period. Participants will be screened for eligibility for up to 6 weeks during the Screening Period. Approximately 36 eligible participants will be randomized in a 2:1 ratio to receive either weight-based IV infusion of ravulizumab (Table 11) or placebo during the double-blind Randomized Controlled Period. Upon completing the last assessment of the Randomized Controlled Period at Week 26, participants may continue into the OLE Period.

For each participant, the Randomized Controlled Period ends and the OLE Period begins at Week 26 (see Section 6.1.1.1 for details). During the OLE Period, participants in the ravulizumab group will continue to receive ravulizumab treatment, and participants in the placebo group will switch to receive ravulizumab treatment. Participants will receive ravulizumab until ravulizumab is registered or approved (in accordance with country-specific regulations) or for up to 130 weeks (approximately 2.5 years), whichever occurs first.

Randomized Controlled Period

All participants randomized into the study are expected to complete the Randomized Controlled Period and will be followed until the end of the Randomized Controlled Period

Participants who discontinue study intervention will complete the Randomized Controlled Period (see Section 7.1). Participants that require acute therapy with standard DM treatment (see Section 6.5.3) due to protocol defined Clinical Worsening (see Section 4.1.3) and complete all remaining visits of the Randomized Controlled Period will be permitted to enter OLE Period.

Participants who discontinue/withdraw from the study will not be permitted to enter the OLE Period (see Section 7.2). Participants who will not enter the OLE Period will not receive an infusion at Week 26.

OLE Period

All participants completing the OLE Period will have an EOS Visit at Week 156 and a follow-up phone call 21 weeks (± 1 week) after the participant's last dose of study intervention to collect information on concomitant medications, non-pharmacologic therapies and procedures, and AEs.

Participants who discontinue study intervention are encouraged to complete the visits and assessments of the OLE Period (see Section 7.1).

Adjustments of 'protocol allowed' DM medications (Section 6.5.1) will be permitted throughout the OLE Period (Section 6.5.1).

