6.1.1.1. Part A

For each participant in Part A, the entire duration is up to 156 weeks, consisting of a Randomized Controlled Period (26 weeks), and an OLE Period (up to 130 weeks, last scheduled dosing at OLE Week 148).

Randomized Controlled Period

Randomized Controlled Period is a double-blind, randomized, placebo-controlled period. Eligible participants will be randomized 2:1 to receive blinded doses of ravulizumab or placebo starting on Day 1 and ending after assessments on Week 26.

- Participants in the ravulizumab group will receive a blinded loading dose of ravulizumab (10 mg/mL formulation) via IV infusion on Day 1, followed by a blinded maintenance dose at Week 2, Week 10, and Week 18 (Table 12).
- Participants in the placebo group will receive a blinded placebo via IV infusion on Day 1, followed by a blinded placebo at Week 2, Week 10, and Week 18.
- Participants who discontinue study intervention will be followed for key efficacy (Section 8.1) and safety assessments (Section 8.2) until the end of the Randomized Controlled Period, withdrawal of consent, or lost to follow-up, whichever is earlier.

Participants who will not enter the OLE Period will complete the assessments for Week 26 but will not receive an infusion at Week 26.

Open-Label Extension Period

The Randomized Controlled Period will end after all predose assessments have been completed at the Week 26 visit. The OLE Period will begin when participants, that elect to continue treatment, receive the Week 26 study intervention infusion. To maintain the treatment randomization blind of the Randomized Controlled Period, participants in both the placebo group and the ravulizumab group will receive blinded doses of ravulizumab as follows:

- Participants in the placebo group will switch to receive a blinded loading dose of ravulizumab (10 mg/mL formulation) at Week 26 (Table 12).
- Participants in the ravulizumab group will receive a blinded ravulizumab dose (10 mg/mL formulation) of 900 mg at Week 26. The 900 mg dose at Week 26 is chosen to maintain complete C5 inhibition over the 2-week period until the next scheduled maintenance dose.

Starting at Week 28, all participants will receive open-label ravulizumab maintenance doses (100 mg/mL formulation) q8w until the last scheduled dose at Week 148 (Table 12).

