8.2.8. Participant Safety Card

Before the first dose of the study intervention, a Participant Safety Card will be provided to participants to carry with them at all times until 5.5 terminal half-lives (8 months) after the final dose of ravulizumab. The card is provided to increase participant awareness of the risk of meningococcal infection and promote quick recognition and disclosure of any potential signs or symptoms of meningococcal infection experienced during the course of the study and to inform participants on what actions must be taken if they are experiencing signs or symptoms of infection.

At each visit throughout the study, the study staff will ensure that the participant has the Participant Safety Card (Section 1.3).

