- Cases of pregnancy that occur during maternal or paternal exposure to study intervention are to be reported within 24 hours of Investigator/site awareness. Data on fetal outcome and breastfeeding will be collected for regulatory reporting and safety evaluation.

Events Not Meeting the AE Definition

- Any clinically significant abnormal laboratory findings or other abnormal safety assessments
 which are associated with the underlying disease, unless judged by the Investigator to be more
 severe than expected for the participant's condition.
- The disease/disorder being studied or expected progression, signs, or symptoms of the disease/disorder being studied, unless more severe than expected for the participant's condition.
- Situations in which an untoward medical occurrence did not occur (social and/or convenience admission to a hospital).
- "Lack of efficacy" or "failure of expected pharmacological action" per se will not be reported as an AE or SAE. Such instances will be captured in the efficacy assessments. However, the signs, symptoms, and/or clinical sequelae resulting from lack of efficacy will be reported as AE or SAE if they fulfil the definition of an AE or SAE.

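### Planned pregnancy data collection stops at the End of Study Visit, leaving about 77% of the protocol's own 8-month post-dose precaution window uncovered for participants who stop after the last scheduled dose

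*Protocol*

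**What the plan says.** Section 10.6.3 sets the planned collection period: pregnancy data are gathered for female participants and "spouses/partners of male participants from the first dose of study intervention until the EOS Visit".

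For Part A, dosing continues "until the last scheduled dose at Week 148" (6.1.1.1), and "All participants completing the OLE Period will have an EOS Visit at Week 156" (4.1.1). For Part B the last scheduled dose is Week 116 (6.1.1.2) and the EOS Visit is Week 124 (4.1.2). Participants who withdraw have an Early Termination Visit 8 weeks after their last dose (7.2).

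The post-dose precautions run much longer. Women of childbearing potential must use contraception, "including at least 1 of the following until at least 8 months after the final dose of study intervention" (10.6.2.1). Section 10.6.2.2 sets 8 months for men, the ova and sperm donation rules use the same period, and Table 6 (2.3.1) does so for breastfeeding. The safety card is carried "until 5.5 terminal half-lives (8 months) after the final dose of ravulizumab" (8.2.8).

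Three other places bear on pregnancy and have no EOS limit:

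- Section 8.2.7 collects details from the start of study intervention and gives no last date for conception.
- Section 10.4.1 says: "Cases of pregnancy that occur during maternal or paternal exposure to study intervention are to be reported within 24 hours" of the site becoming aware.
- Section 10.6.3.2 requires exposed pregnancies to be recorded and followed to outcome, even after withdrawal.

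The one contact planned after EOS is a call at 21 weeks (± 1 week) after the last dose. It covers concomitant medications, non-drug therapies and procedures, and AEs.

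**The concern.** Table 6 lists pregnancy exposure as a potential risk and gives the reason: "No studies of ravulizumab have been conducted in pregnant or breastfeeding women". In a programme of about 150 participants (36 in Part A and 114 in Part B) exposed pregnancies will be few, so each one and its outcome is worth having.

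The protocol asks participants to behave as though the drug still matters for 8 months, but it plans to gather pregnancy information for only the first 6 to 8 weeks of that time. After that, no scheduled contact asks about pregnancy. An uncomplicated pregnancy is ordinarily not an AE (10.6.3), so the AE question on the 21-week call need not bring it out. What remains is reporting when the site happens to learn of a pregnancy, under sections that state their scope differently from 10.6.3.

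**Working it through.** **Inputs.** Last dose and EOS weeks are from 6.1.1.1, 6.1.1.2, 4.1.1 and 4.1.2. The printed Part A days are from Table 4 of the Schedule of Activities, whose day row reads "D757 | D813 | D869 | D925 | D981 | D1037 | D1079". The 8-month window is from 8.2.8, 10.6.2.1, 10.6.2.2 and Table 6. The 21-week call is from 4.1.1, 4.1.2 and 7.2.

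**Step 1: last dose to EOS.** Study day = 1 + 7 × week.

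- Part B: Week 116 is Day 813 and Week 124 is Day 869, so 869 − 813 = 56 days. This matches the printed days.
- Part A by week label: Week 148 is Day 1037 and Week 156 is Day 1093, so 56 days.
- Part A by printed day: 1079 − 1037 = 42 days. Day 1079 is (1079 − 1)/7 = Week 154, not Week 156. The label and the day disagree and must be reconciled.

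**Step 2: length of the window.** 8 × 365.25/12 = 243.5 days, or 243.5/7 = 34.8 weeks.

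**Step 3: share of the window after planned collection ends.** Share = (243.5 − d)/243.5, where d is days from last dose to the end of collection.

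| End of collection | d (days) | Days left | Share uncovered |
|---|---|---|---|
| EOS by week label, both parts | 56 | 187.5 | 77.0% |
| EOS by Part A printed day | 42 | 201.5 | 82.8% |
| Latest EOS (week label, +7 days) | 63 | 180.5 | 74.1% |
| Earliest EOS (printed day, −7 days) | 35 | 208.5 | 85.6% |
| 21-week call, if it asked about pregnancy | 147 | 96.5 | 39.6% |
| The same call at 22 or 20 weeks | 154 or 140 | 89.5 or 103.5 | 36.8% or 42.5% |

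Taking 8 months as anything from 240 to 248 days moves the main shares by less than 1.5 percentage points (for example 76.7% to 77.4% at 56 days).

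**Step 4: one case through the text.** Suppose a participant or partner conceives 4 months (about 122 days) after the final scheduled infusion.

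- This is inside the contraception window of 243.5 days.
- It is after EOS at day 56, so outside the period set in 10.6.3.
- The call at day 147 comes about 25 days later and does not list pregnancy.
- Section 10.6.3.1 covers partner pregnancies only while the man is in the study, and the opening rule of 10.6.3.2 has a similar limit.
- If the site does learn of it, 10.4.1 and the general rule in 10.6.3.2 point towards reporting and follow-up. For former participants, though, 10.6.3.2 spells out only related pregnancy SAEs and says the investigator need not look for them.

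**The case against.** The strongest reply is that the sections are compatible. Section 10.6.3 can be read as the period of planned collection, with 10.4.1 and 10.6.3.2 adding duties triggered by awareness or exposure. A site can comply with all of them. Section 8.3.1 also requires related SAEs learned of after discharge to be notified, and complications and abnormal outcomes of pregnancy count as AEs or SAEs, so those known by the 21-week call fall within its scope. This stands. A reader might infer that sites may properly leave a known exposed pregnancy unreported, or that the sections give opposite instructions. The text does not support either reading. What it does allow is not asking.

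A reader might also infer that most exposed pregnancies after treatment would be missed. The documents do not support that. The 77% is a share of calendar time, no conception rate is given, and turning time into pregnancies would need a uniform rate over the window. Awareness-based reporting would also catch some.

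Two further limits are fair. First, no section defines pregnancy exposure as lasting 8 months. The half-life statement belongs to the meningococcal safety card, and the other 8-month figures are precautions. Reading them as the relevant exposure period is reasonable, but it is an inference.

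Second, the 77% does not apply to everyone. Participants who stop dosing in the RCP but stay on study are followed for longer: in Part B, a last dose at Week 2 with visits to Week 50 gives 48 weeks, more than the 34.8-week window. Those who stop in the OLE are encouraged to complete its visits. Those who move to approved product or a rollover study may remain on treatment, so the post-dose window has not begun.

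**Conclusion.** The point holds as a gap in planned collection. Section 10.6.3 stops pregnancy data at the EOS Visit. For participants who take the last scheduled dose and then stop ravulizumab, about 77% of the protocol's 8-month precaution window has no planned pregnancy collection (83% by Part A's printed days; 74% to 86% across the ± 7-day visit windows). Counting the 21-week call as though it asked about pregnancy would still leave about 40%.

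The result rests on two assumptions: that the 8-month precaution period is the right yardstick for post-dose exposure, and that EOS takes place at its scheduled time. How many pregnancies would go unrecorded cannot be estimated from the documents. The efficacy analyses are not affected. This is an inexpensive improvement to safety data and should be made.

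**What to change.** - In 10.6.3, end collection 8 months after the final dose of study intervention instead of at the EOS Visit. This is the protocol's own figure.
- In 10.6.3.1 and 10.6.3.2, align the wording that ties collection to being in the study, so that it covers the same period.
- In 8.2.7, add the same end point; that section now gives none. Its references to Section 10.5 and 10.5.3 for pregnancy procedures should also be corrected, because Section 10.5 now covers medication error, drug abuse and drug misuse, and pregnancy is in 10.6.
- Add participant and partner pregnancy to the items asked at the existing 21-week call.
- At the last visit, ask participants to report any conception up to 8 months after the final dose. This covers the roughly 14 weeks after the call (96.5/7 = 13.8).
- Reconcile the Part A EOS label (Week 156) with its printed day (Day 1079).

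The cost is protocol wording, one question on an existing call, and a longer period in which sites forward the existing pregnancy form. No visit or test is added.
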